**Analysis visit** is the visit label derived based on study day of assessment and the analysis visit windows defined in Table 2-1. For laboratory and bioanalytical parameters specified for both Group 1 and Group 2 in Table 2-1, two sets of analysis visits will be derived and will be referred to as "**AV1**" and "**AV2**" respectively. The AV1 is derived according to Group 1 for by visit analysis on full analysis set (FAS). For AV2, assessments >14 days after the last dose date will be slotted into the analysis visit window for follow up visit for by-visit analysis of laboratory data on safety analysis set (SAF).

**Analysis visit windows** are non-overlapping periods each associated with a visit planned in protocol and all together cover the entire study period of a patient. If multiple measurements of same parameter for a patient fall in the same window, the value of this analysis visit is selected according to Table 2-2. If no assessment falls into a window, the value of that analysis visit will be set to missing unless imputation rule(s) are defined for the parameter. Repeat and unscheduled visits will be mapped to analysis visits in the same way as scheduled visits.

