All practical measures will be exercised in the study to collect as much data as possible at week 48 despite intercurrent events (e.g. early discontinuation of study treatment). In the case of early withdrawal from the study on or after week 24, patient's histological response will be assessed if possible at the early termination visit.

A combination of the while-on-treatment and hypothetical strategies as defined in ICH E9 (R1) on handling intercurrent events will be adopted for the primary analysis.

If a patient discontinued study treatment early or withdrew early from the study without other inter-current event, but has histological response status collected after at least 24 weeks of study treatment, the primary endpoint will be imputed with their last histological response status

Novartis	For business use only	Page 20
SAP		CLJN452D12201C

assessed after at least 24 weeks of treatment. Patients with missing primary endpoint or primary endpoint after inter-current event(s) will have their primary endpoint data imputed with a multiple imputation (MI) method as outlined in Section 2.5.3 to estimate the treatment effect that would have been observed if all patients had continued on treatment for 48 weeks without intercurrent event.

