With the sample data collected in the study, the naive differences  $P_1-P_{2i}$  can be estimated using  $p_1-p_{2i}$  with unpooled standard error SE = sqrt(  $p_1*(1-p_1)/n_1 + p_{2i}*(1-p_{2i})/n_{2i}$ ).

The hierarchical testing procedure based on odds ratio can be formulated as one-sided statistical tests ( $\alpha$ =0.05) for

H0i: 
$$\frac{P1(1-P2_i)}{P2(1-P1_i)} \le 1$$
 vs. H1i:  $\frac{P1(1-P2_i)}{P2(1-P1_i)} \ge 1$ 

executed sequentially for i=(1, 2), where H02 is tested only if H01 is rejected.

A logistic regression model with the logit of probability for histological response as the dependent variable, treatment groups as the main effect, baseline fibrosis stage (2 vs. 3) and T2DM (No/Yes) status as co-factors, and baseline BMI as a covariate will be utilized to test the hypothesis at each step of the hierarchical testing procedure.

The choice of co-factors/covariates, the considerations for their collinearity, potential interactions with treatment effect and model specifications are further discussed in Section 5.4.1.

The logistic regression analyses can be implemented in SAS LOGISTIC procedure with the *scale=williams* and *firth* options in the model statement, executed together with the multiple imputation (MI) methods outlined in Section 2.5.3.

Odds ratios and 95% CI of the probabilities of histologic response between study treatments can be back calculated as the exponentiation of the corresponding coefficients estimated from the logistic regression.

One logistic regression model can be fitted on all FAS data from the three treatment arms to estimate the pairwise odds ratios and associated p-values.

Given placebo effects (Table 3-1) reported in the published literature and with Firth correction, a model convergence issue is not expected. In the case a convergence issue occurs and cannot be resolved with other appropriate technical approaches, a reduced model may be used for the primary analysis. The reduced model will be determined by removing baseline BMI, fibrosis stage and T2DM status sequentially from the full model until the convergence issue is resolved. If a reduced model has to be used, impacts on the interpretation of primary analysis results will be discussed in the core CSR in combination with results from sensitivity analysis.

Existence of extremely influential baseline BMI values will be examined with Cook's distance plot based on complete cases before MI.

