# 2.5.3 Handling of missing values/censoring/discontinuations

Especially due to the clinical burden of liver biopsy, missing data is possible and could be related to observable data or even the unobserved primary endpoint.

While not possible to confirm missing completely at random (MCAR), the histological response status from the early termination visit after at least 24 weeks of study treatment will be used for the primary analysis in case of missing primary endpoint at week 48. Patients otherwise with primary endpoint missing or any primary endpoint after intercurrent events will have the values imputed using multiple imputation (MI) methods (Rubin 1976, 1987) under a missing at random (MAR) assumption.

An arbitrary missing pattern will be assumed and a fully conditional specification (FCS) method with logistic regression will be applied. Baseline fibrosis stage (2 vs. 3), baseline T2DM (No/Yes), baseline BMI (as categorical predictor) and decrease of ALT at week 24 ( $\leq$  -17 U/L vs. >-17 U/L) will be included as predictors for the imputer's model. The logistic model outlined for primary analysis will be used to analyze the multiply imputed datasets, and pooled results will be obtained based on Rubin's combination rules.

More details for the MI method are discussed in Section 5.4.2.

The MI methods may be implemented using the SAS MI procedure with FCS LOGISTIC statement and the MIANALYZE procedure. The order of variable imputation will be specified with ORDER=VAR option in FCS statement. The VAR statement will list variables for baseline fibrosis stage (2 vs. 3), baseline T2DM status (No/Yes), baseline BMI (as continuous predictor) and decrease of ALT at week 24 (<= -17 U/L vs. >-17 U/L) in sequence. The number of imputations will be set to 50.

The number (%) of patients with missing primary endpoint at week 48 will be summarized by study treatment.

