- 4.6 For secondary **analysis** analysis using repeated measurement ANCOVA model, inclusion of interaction between time (visit) and treatment are explicitly clarified. This change is to ensure consistent implementation of the analysis to account for the possibility that treatment effects change over time.
- 4.7 Additional sensitivity analysis for the primary endpoint based on CMH test is added (Section 2.5.4), given its robustness against risk of potential misassumption for the logistic regression for primary analysis. This change is implemented also in response to FDA comments.
- 4.8 Multiple imputations will be performed based on FCS with logistic regression instead of discriminant function (Section 2.5.3). This change is implemented for the convenience of including dichotomous predictors in the imputer's model.

Novartis SAP	For business use only	Page 35 CLJN452D12201C
4.9	Multiple imputations will be implemented by excluding treatment imputer's model instead of performing MI separately within ea (Section $2.5.3$ ). This change helps to reduce the computational implementation and enables more complete cases for the MI.	ach treatment group
4.10		
4.11	Demographics and baseline characteristics summary will be on $2.3$ ). This change is implemented in the spirit of lean SAP beca difference between SAF and FAS is expected.	•
4.12	Listing of safety data pre- or post treatment will not be product implemented in the spirit of lean SAP and such listings are cor- for the objectives of the study. To support data review and wri- informal listings can be used.	nsidered not essential

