#### 5.4.2 Multiple imputation for missing primary and key secondary analysis

MI method for missing data allows the flexibility of including additional auxiliary variables in the imputer model and accounts for the uncertainty on real value with multiple inputted values.

For the binary dependent variable, a Fully Conditional Specification (FCS) logistic regression method is chosen for the imputer model considering the convenience of including dichotomous predictors. Baseline fibrosis stage (2 vs. 3), baseline T2DM (No/Yes), baseline BMI (as

Novartis
SAP

categorical predictor) and decrease of ALT at week 24 ( $\leq$  -17 U/L vs.  $\geq$ -17 U/L) will be included as predictors for the imputer's model.

The exclusion of treatment from the imputer model ensures a more conservative estimate of treatment effect in that it would bias only toward null (for superiority test) if a relationship between treatment and response does exist (Schafer 1997). The inclusion of decrease in ALT at week 24 (<= -17 U/L vs. >-17 U/L) into the imputer's model is based on findings by Loomba et. al. (2019) and considering the balance between general validity of analysis model and some loss in precision in case a trivial factor is additionally added in imputer's model (Rubin 1996).

If a reduced logistic regression model has to be adopted (Section 2.5.2), the reduced list of predictors in primary analysis model will also be used for the imputer model, except for the treatment which will still be excluded.

The imputer's model is first fitted using observations  $(n_0)$  with non-missing data

logit (p) = 
$$\beta^{T} \mathbf{X}$$

where

p is the true probability of response

**X** is the  $n_0$  by p matrix of covariates

 $\beta$  is the vector of coefficients to be estimated as the first step of MI.

Based on the estimated regression coefficients  $\hat{\beta}$  and associated covariance matrix, posterior predictive distribution for  $\beta$  is built and a new set of parameters  $\beta_{\#}$  is randomly sampled from it.

For *i*th patient with missing data, expected probability  $q_i = \Pr$  (response) is calculated as

$$q_i = \frac{\exp(\boldsymbol{\beta}_{\#}^{\mathsf{T}} \boldsymbol{X}_i)}{1 + \exp(\boldsymbol{\beta}_{\#}^{\mathsf{T}} \boldsymbol{X}_i)}$$

and this patient's response status will be imputed as Yes if  $q_i$  is larger than a random number sampled from uniform distribution between 0 and 1.

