These imputation steps can be implemented using SAS MI procedure. A total of  $\geq$ =50 iterations of imputations will be executed to create 50 imputed complete data sets.

The logistic regression model for primary or key secondary analysis is then executed separately for these data sets with results (parameter estimates) stored in an output data set.

The SAS MIANALYZE procedure reads in the parameter estimates, standard errors or covariance matrix in the output data set generated by the logistic regression analyses, and produces estimates and 95% confidence limits to back calculate the odds ratios (95% CI). P-values will be presented if formal hypothesis test is to be performed according to hierarchical testing procedure outlined in Sections 2.5 and 2.6.

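### SAP 5.4.2 imputes missing histology without randomised treatment but analyses it with treatment: at 10% imputed the log odds ratio shrinks about 10% and power falls about 6 points, less where Week 24 ALT carries the effect

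*SAP*

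**What the plan says.** SAP 2.5.3 and 5.4.2 describe one imputation model for all arms: "An arbitrary missing pattern will be assumed and a fully conditional specification (FCS) method with logistic regression will be applied". Its predictors are baseline fibrosis stage, T2DM status, BMI and a Week 24 ALT decrease split at 17 U/L. Treatment is left out on purpose. SAP section 4, item 4.9, lists this as a departure from the protocol ("Multiple imputations will be implemented by excluding treatment") in place of imputing within each arm, to save computation and keep more complete cases. SAP 5.4.2 gives a statistical reason: "The exclusion of treatment from the imputer model ensures a more conservative estimate of treatment effect in that it would bias only toward null". If the analysis model has to be reduced, the imputer takes the same reduced predictor list, "except for the treatment which will still be excluded".

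The analysis model in SAP 2.5.2 has "treatment groups as the main effect". SAP 5.4.2 says: "The logistic regression model for primary or key secondary analysis is then executed separately for these data sets". The results are pooled by Rubin's rules.

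Under SAP 2.5, imputation covers missing endpoints and endpoints after an intercurrent event. A patient who stopped early "without other inter-current event, but has histological response status collected after at least 24 weeks of study treatment" keeps the observed result. The stated aim is the effect had everyone stayed on treatment for 48 weeks with no intercurrent event.

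This SAP dates from December 2019 and describes three arms and 210 patients. Protocol v02 has four arms and 380 participants. Its section 12.4.4 keeps FCS logistic imputation and sends the details to the SAP.

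**The concern.** An imputation model should contain every term in the analysis model. When treatment is missing from the imputer, imputed outcomes carry a treatment effect only through Week 24 ALT. Otherwise they are drawn at a common rate, and each comparison is diluted by roughly the imputed fraction. That misses the target in SAP 2.5.

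Week 24 ALT could offset the dilution, because protocol 1.1.3 and 1.1.4 report that both drugs lower ALT. It cannot help patients who have no assessment in the Week 24 window (days 156-197 in SAP Table 2-1). For them SAP 2.1.1 applies: "If no assessment falls into a window, the value of that analysis visit will be set to missing". In the FCS step their ALT is then itself imputed without treatment.

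At stake are a diluted odds ratio and lost power in the primary and key secondary tests. SAP 3.1 makes no sample-size allowance for dropout, on the ground that imputation will handle it.

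**Working it through.** **1. Reproduce the plan's power.** SAP Table 3-2 gives 80% for 45% vs 25%, with n = 70 per arm and one-sided 0.05.
- Null SE = √(2 × 0.35 × 0.65 / 70) = 0.0806.
- Alternative SE = √((0.25 × 0.75 + 0.45 × 0.55) / 70) = 0.0788.
- z = (0.20 − 1.645 × 0.0806) / 0.0788 = 0.855, so power is 80.4%.

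The 40% vs 20% and 50% vs 30% rows give 83.2% and 78.4% (stated: 84% and 79%). These are complete-data figures.

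**2. Closed-form dilution.** The only rate the SAP states is 10% dropout (3.1); it is taken here as the imputed share m. With no information from ALT, an arm's rate becomes p′ = (1 − m)p + m·p̄.
- p̄ = (0.45 + 0.25 + 0.25) / 3 = 0.3167.
- Combination: 0.9 × 0.45 + 0.1 × 0.3167 = 0.4367. Monotherapy: 0.9 × 0.25 + 0.1 × 0.3167 = 0.2567.
- The log odds ratio falls from 0.898 to 0.809, a shrinkage of 9.9%.

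**3. Simulated power.** Three arms of 70, 50 imputations, Firth logistic analysis, Rubin pooling. Missingness is random within arm, baseline covariates are unrelated to response, and ALT is linked to response only (drop in 60% of responders, 40% of non-responders). Both imputers were run on the same data; 4,000 to 10,000 trials per case; Monte Carlo error of each power is about 0.5 to 0.8 points.

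| Rates | Imputed | Shrinkage | Power without treatment | Power with treatment |
|---|---|---|---|---|
| 45% vs 25% | 10% | 9.8% | 0.70 | 0.76 |
| 40% vs 20% | 10% | 9.9% | 0.72 | 0.78 |
| 50% vs 30% | 10% | 9.7% | 0.67 | 0.73 |
| 45% vs 25% | 5% | 4.9% | 0.74 | 0.77 |

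A second simulation gave losses of 5.9, 5.7 and 6.5 points for the three 10% rows. Against complete data the total loss there was about 9 to 10 points. At 20% imputed (50% vs 30%) it gave 19.9% shrinkage and 14.7 points lost against imputation with treatment.

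In the 45% vs 25% case at 10% imputed, the mean Rubin SE is 0.391 without treatment and 0.395 with it, so adding treatment does not narrow the intervals. Without treatment the estimator's sampling SD is 0.349, and 0.391 / 0.349 = 1.12: the Rubin SE is about 12% too large.

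**4. How far ALT offsets this** (45% vs 25%, 10% imputed).
- ALT observed, with the drop 15, 30 or 45 points more frequent on combination and 20 points more in responders: shrinkage 8.2%, 6.2%, 3.9%; power loss 4.5, 2.7, 0.5 points.
- Half of those imputed lack Week 24 ALT, 30-point link: 8.1% and 4.1 points.
- None has Week 24 ALT: 9.7% and 6.0 points.

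**5. Direction and type I error.**
- True null, 30% in every arm, 10% imputed: rejection 3.0% without treatment, 4.5% with it.
- Unequal shares: combination and licogliflozin both 40%, tropifexor 20%, 5% imputed on combination and 15% on licogliflozin. With p̄ near 0.333, the rates become 0.95 × 0.40 + 0.05 × 0.333 = 0.397 and 0.85 × 0.40 + 0.15 × 0.333 = 0.390. The odds ratio is 1.03 where the truth is 1; rejection 4.1%.
- Combination lowers ALT (45 points; responders +30) without changing histology: mean odds ratio 1.06 without treatment, 1.00 with it; rejection 5.1% vs 4.9%.
- Extreme link (60 points; responders +30) with a true effect: the estimate is 2.4% too large.

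**6. Protocol v02** (140/80/80/80, Table 12-3 rates, two-sided 0.025). The shares of 3% and 5% are assumptions. At 3%:
- Fibrosis endpoint: p̄ = (140 × 0.35 + 160 × 0.30 + 80 × 0.20) / 380 = 0.297, closed-form shrinkage 3.3%. Simulation: 3.2%, power 0.48 vs 0.52.
- NASH-resolution endpoint: p̄ = (140 × 0.25 + 160 × 0.20 + 80 × 0.10) / 380 = 0.197, closed-form shrinkage 3.7%. Simulation: 3.8%, power 0.60 vs 0.64.
- With an ALT link (drop in 55% on combination, 40% on monotherapies and 20% on placebo, plus 20 points in responders): losses of 1.7 and 2.0 points.

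At 5%, without the ALT link: losses of 4.7 and 6.2 points.

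**The case against.** The strongest case is that this is a disclosed, deliberate trade-off. The SAP names the direction of the bias and accepts it, type I error is not inflated, and SAP 2.5.4 has non-responder and CMH analyses that do not use this imputer. That is fair as to candour and error control. But the size is nowhere stated, and disclosure does not bring the estimator to its target. The SAP already has a labelled conservative analysis, so the primary one need not be diluted. The reasons in item 4.9 compare with separate imputation by arm. Treatment is known for every randomised patient, so as a predictor in the single model it loses no complete cases.

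The quoted rationale also carries a condition: it applies when treatment and response are related. The ALT-without-histology case falls outside that condition. The 60-point link is implausible, since at most 10% of monotherapy non-responders could then show the ALT drop, while the protocol says both monotherapies lower ALT. The unequal-share case remains: treatment affects response in the trial, yet a null pair moves off 1. The movement is small.

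The headline figures belong to a superseded design, and this stands. Protocol 2.1 and 12.4.3 now use treatment-policy and composite strategies, and count stopping before Week 24 or having no Week 48 biopsy as non-response. Few outcomes may be left to impute. The share is unsettled, however. Protocol 12.4 limits imputation to missing data unrelated to intercurrent events, 12.4.4 also imputes endpoints after them, and 12.8.1 expects about 20% missing biopsies.

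Finally, 10% dropout is not the imputed share, and the documents give no ALT difference between combination and monotherapy. Both points stand, so the result is a range.

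**Conclusion.** The concern holds. The imputer omits the main term of the analysis model, so the log odds ratio shrinks by about the imputed fraction unless Week 24 ALT carries the effect. In the SAP's design at 10% imputed, with ALT informative only through response, that is about 10% shrinkage and about 6 points of power, compared with the same missing data imputed with treatment in the model. With ALT observed and linked to treatment, the loss ranges from 4.5 points down to 0.5 over links of 15 to 45 points.

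The harm is a diluted estimate and lost power. It is not type I error and not lost precision. The claim that bias can run only toward the null is not guaranteed, though the departures found were small.

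The mechanism is certain. The size rests on the assumed imputed share, missingness at random within arm, and assumed ALT links. Williams scaling was not simulated. For protocol v02 the figures are hypothetical until the imputed share is stated. This should be corrected in the SAP update that v02 requires anyway.

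**What to change.** When the SAP is updated to protocol v02:
- Add randomised treatment (all arms) as a predictor in the single FCS logistic imputation model in 2.5.3, 4.9 and 5.4.2. This includes the step that fills missing Week 24 ALT and the sentence on the reduced model. Keep the other predictors.
- Delete the rationale that bias runs only toward the null.
- Keep the non-responder analysis in 2.5.4 as the labelled conservative analysis.
- State the share expected to be imputed after the 24-week reuse rule and the non-responder rules in protocol 12.4.3.

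The cost is one term in the imputation statement: two extra imputer parameters with three arms or three with four, and Rubin standard errors about 1% larger at 10% imputed (0.395 / 0.391 = 1.01).

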#### 5.4.3 Repeated measurement ANCOVA (MMRM) for secondary analyses

Suppose the continuous dependent variable vector  $y_i = (y_{i1}, ..., y_{im_i})'$  of a patient i = 1,...,n observed at different time points (visits)j=1, ..., m follows a *m*-dimensional multivariate normal distribution with some non-trivial off-diagonal elements in its  $m_i \times m_i$  variance - covariance matrix.

The MMRM is chosen because it can explicitly account for such correlation and non-constant variability in data with a schematic model

#### $Y = X\beta + Z\gamma + \epsilon$

where

 $X \sim covariates of fixed effects (including treatment effect of interest) with coefficients vector <math>\beta$ 

 $Z \sim random \ effects \ with \ coefficients \ \gamma \ normally \ distributed \ with \ expected \ value \ 0 \ and \ covariance \ matrix \ (G)$ 

 $\varepsilon \sim$  is random error not accounted for in the model with expected value  $\theta$  and a covariance matrix (**R**)

It follows that the variability of Y can be structured as V=ZGZ`+R for parameterization.

The parameterization of the covariance matrix structures for repeated measurements could be pre-specified based on trial design and assumptions. For analysis in this study, an unstructured covariance matrix is assumed. In case of failure to converge that cannot be resolved with other approaches, compound symmetry structure may be used if it resolves the issue.

Both covariance parameters and the fixed/random effects (including 95% confidence limits) can then be estimated based on likelihood methods, such as the restricted maximum likelihood (REML) method which accommodates the situation of some data missing at random (Rubin 1976; Little 1995) and will be adopted in this study.

The analysis can be implemented in the SAS MIXED procedure with TYPE=UN and subject=<patient ID> in the REPEATED statement and DDFM=KR in model statement. The REML is the default method.

Model assumptions will be checked based on diagnostic plots and influence diagnostics if necessary. The possible impact of questionable models will be discussed in CSR if needed.

